7.3.2. Statistical Analysis for Bioequivalence

7.3.2.1. Variance Analysis (ANADEVA)

The general linear model of the analysis of variance that represents the experimental design for the analysis of data of the adjusted pharmacokinetic variables will be used, considering the following sources of variation in an additive way:

- ✚ Dosing sequence.
- ✚ Nested subjects in the dosing sequence call inter-subject variability or inter-subject residual variability.
- ✚ Dosing period.
- ✚ Therapy or formulation.
- ✚ Experimental error, called intra-subject variability or intra-subject residual variability.

This general lineal model, applied to the crossed designs to determine bioequivalence is the following:

$$Y_{ijk} = \mu + G_k + S_{jk} + P_j + F_{(j,k)} + e_{ijk} \quad (\text{Chow \& Liu, 2009})$$

Where:

μ = general mean.

G_k = fixed effect of k^{th} sequence.

S_{jk} = randomized effect of the i^{th} subject in the k^{th} sequence, where $i = 1, 2, \dots, n_k$ and $k = 1, 2, \dots, K$

P_j = fixed effect of the j^{th} period, where $j = 1, 2, \dots, J$ y $\sum_j P_j = 0$

$F_{(j,k)}$ = direct fixed effect of the formulation in the k^{th} sequence, which is given in the j^{th} period and $\sum F_{(j,k)} = 0$

e_{ijk} = randomized error (intra-subject) in the observation Y_{ijk}

The sequence effect should be assessed using the square means of the nested subject in the sequence as a term of error. All other main effects should be assessed against the residual error (error square mean) and F values reported as appropriate. Additionally, it should be stated if the source of variation is significant when p is < 0.05 ($p < 0.05$).

In the event of a significant effect in the variability factors for the sequence or period, actions will be taken in accordance with the NOM-177-SSA1-2013.

7.3.2.2. Hypothesis Statement for the double, one-sided Schuirmann's t test,

The double, one-sided t test (Schuirmann) will be done with the obtained data from the logarithmic transformation for the $AUC_{0-t}(\text{aj})$ and $C_{\text{max}}(\text{aj})$, by means of the 90 % CI construction for the quotient between the average pharmacokinetic parameters logarithmically transformed from the test and reference drugs.

$$H_0: \mu_p / \mu_r \leq L_i \text{ or } \mu_p / \mu_r \geq L_s$$

$$H_1: L_i < \mu_p / \mu_r < L_s$$

Null hypothesis for bioequivalence is rejected if Schuirmann's P probability $P(t)$ for the lower limit ($L_i = 0.8$) and upper ($L_s = 1.25$) is $P < 0.05$.

7.3.2.3. Determination of the Classical 90 % confidence Interval

Compliance with the *Guide to Establish Interchangeability of Oral Solid Drugs containing Levothyroxine Sodium* (COFEPRIS, 2017). The pharmacokinetic parameters that will be used for the statistical analysis of bioequivalence are $C_{max\ (aj)}$ and $AUC_{0-t\ (aj)}$ of levothyroxine (T4), by means of 90 % confidence intervals for the geometric means of these pharmacokinetic parameters to check their bioequivalence. The classical 90 % confidence interval will be calculated by means of the following equation for the lower and upper limit, respectively.

$$\left[\exp \left(\bar{Y}_T - \bar{Y}_R - t_{1-\alpha, n_1+n_2-2} \hat{\sigma}_w \sqrt{\frac{1}{2} \left(\frac{1}{n_1} + \frac{1}{n_2} \right)} \right), \exp \left(\bar{Y}_T - \bar{Y}_R + t_{1-\alpha, n_1+n_2-2} \hat{\sigma}_w \sqrt{\frac{1}{2} \left(\frac{1}{n_1} + \frac{1}{n_2} \right)} \right) \right]$$

Where:

\bar{Y}_T = population media for the assessed pharmacokinetic parameter of the test drug.

\bar{Y}_R = population media of the assessed pharmacokinetic parameters of the reference drug.

$\hat{\sigma}_w$ = square root of the square mean for the error of the assessed pharmacokinetic parameter.

$t_{(1-\alpha, N-2)}$ = distribution of the Student's t with an α probability of 0.05 and $N-2$ degrees of freedom (df) = $N - 2$ with an α probability = 0.1

n_1 = number of volunteers in the sequence 1.

n_2 = number of volunteers in the sequence 2.

The statistical analysis to show interchangeability will be done using only the corrected values of the parameters for $C_{max\ (aj)}$ and $AUC_{0-t\ (aj)}$, equivalence margins will be considered as 80 % - 125 %.

7.3.3. Outliers

An analysis to identify the outliers (extreme values) based on the estimation of the Student intra-subject residual values will be done using Excel software. By means of the determination of the residual value obtained with the model using the following equation:

$$\widehat{e_{ijk}} = Y_{ijk} - \widehat{Y}_{ijk}$$

Where:

Y_{ijk} is the observed response.

\widehat{Y}_{ijk} is the estimated value with the model.

This residual value should be in the Student fashion by using the following equation:

$$\widehat{e_{jklstd}} = \frac{\widehat{e_{ijk}}}{\sqrt{\left(\frac{S-1}{2 \cdot S} * CMerror \right)}}$$

Where:

$\widehat{e_{ijk}}$ is the residual value previously determined.

S is the number of subjects considered for the assessment

$CMerror$, value of the mean square value of error, corresponding to each of the assessed pharmacokinetic parameters.

Determination of outliers will be done for the pharmacokinetic parameters of C_{max} , and AUC_{0-t} for both analytes.

Criterion: data which extent is higher than ± 2 intra-subject standardized residual values will be considered outlier (extreme).

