5.5. Confidentiality, responsibility and compensation

Information collected in this study will be exchanged exclusively between Merck, S.A. de C.V. and the PPD and will be treated as confidential.

Subjects will sign a consent specifying that they will receive an economical compensation for their participation in the study. The Sponsor will pay (o compensate, if applicable) the resulting injuries or diseases caused by the subjects' participation in the study until their resolution according to the medical opinion. The Sponsor will not pay if this is due to the subject's negligence, irresponsible conduct or medical conditions no related to the study.

The Ministry of Health, the Ethics and Investigation Committee and the Investigation Committee will be the only authorized bodies for reviewing the study documents (including the participant subjects' identity data) and the documents considered confidential by the PPD

and Merck, S. A. de C. V.

Study participant subjects' personal data will be confidential and will be protected by the Federal Law on the Protection of Personal Data held by Private Parties, which is stated in our PRIVACY NOTICE and can be checked in our website www.cecype.com.

6. Samples Chemical Analysis

Levothyroxine (T4) serum concentrations will be determined by liquid chromatography coupled in a mass detector/mass according to the physicochemical properties and reported in the international scientific literature (LC MS/MS), which will be validated prior to the start of the study according to the applicable guidelines and the study working plan, as well as to the applicable analytical technique, in compliance with the applicable Analytical Unit and Quality Assurance procedures, and according to the NOM-177-SSA1-2013 and the Good Laboratory Practice. The analytical method details will be described in the validation protocol.

7. Sample Size Determination, Pharmacokinetic and Statistical Analysis

The pharmacokinetic and statistical analysis for the levothyroxine serum concentrations will be carried at the PPD as per its standard operating procedures and in compliance with the NOM-177-SSA1-2013.

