7.2. Pharmacokinetic Analysis

The pharmacokinetic analysis will be obtained by using a non-compartmental analysis with the use of the current versions of the Phoenix® WinNonlin® software.

The following parameters will be determined. They will be calculated with the uncorrected data of the baseline levels (raw values), as well as the corrected values by baseline levels (adjusted values). The mean of the pre-dose levothyroxine levels should be used for the baseline adjustment of the post-dose levels. Any negative values obtained from baseline correction should be designated as zero (0):

C_{max}: maximum serum concentration observed directly from the concentration-time curve.

C_{max(aj)}: maximum serum concentration in pre dose corrected data.

t_{max}: time when the maximum serum concentration was obtained.

AUC_{0-t}: area under the curve of the serum concentration as a function of time, from time 0 until the last sampling time by means of the trapezoidal rule.

AUC_{0-t (aj)}: area under the curve of the serum concentration as function of time, from time 0 until the last sampling, by means of the trapezoidal rule in pre dose corrected data.

$$AUC_{0-\infty (aj)} = AUC_{0-t (aj)} + C_{t (aj)} / K_{el}$$

K_{el}: elimination constant, calculated from the semi-logarithmic graphic of the serum concentration as function of time. It is estimated by means of a simple linear regression analysis from at least the last three serum concentrations different to zero.

t_{1/2}: time of the half-life or elimination half-life calculated as $\ln (2) / K_{el}$

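### Section 7.3.3 names the outlier-screen variables incorrectly: plain Cmax and AUC0-t for two analytes, where the rest of section 7 models and decides on baseline-adjusted T4 only

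*Protocol*

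**What the plan says.** All references are to the protocol.

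- **7.3.3, variables.** "Determination of outliers will be done for the pharmacokinetic parameters of" Cmax and AUC0-t "for both analytes". Neither the (aj) suffix nor the word adjusted or corrected appears.
- **7.3.3, calculation.** The residual is introduced with "By means of the determination of the residual value obtained with the model using the following equation". It is divided by the square root of (S-1)/(2S) times the error mean square, where "S is the number of subjects considered for the assessment". A standardised residual beyond ±2 is an outlier.
- **7.2.** Plain Cmax is the "maximum serum concentration observed directly from the concentration-time curve". Cmax(aj) and AUC0-t(aj) have separate entries for baseline-corrected data.
- **7.3.2.1.** The linear model for "analysis of data of the adjusted pharmacokinetic variables will be used".
- **7.3.2.3.** "The statistical analysis to show interchangeability will be done using only the corrected values of the parameters" Cmax(aj) and AUC0-t(aj).
- **Section 6.** "Levothyroxine (T4) serum concentrations will be determined by liquid chromatography" with mass detection. No other analyte is assayed for the pharmacokinetic analysis.
- **Table 2 (section 2.1).** The baseline-adjusted parameters are the primary endpoints. Plain AUC0-t and Cmax are listed as secondary.
- **7.3.4.** Section 7.3 is declared to be the statistical plan. Data may be removed only in listed cases, of which the 7.3.3 criterion is one, and outlier exclusion needs scientific support. The reference geometric mean in the 5 % low-concentration rule is calculated without outliers.

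**The concern.** An outlier screen for a bioequivalence decision should examine the values that enter the decision. T4 is endogenous, so an uncorrected parameter mixes the subject's own hormone level with the dose increment. A change in baseline between periods can produce a large raw residual that baseline correction would reduce. Conversely, an aberrant adjusted value can be diluted by the endogenous level and go unflagged.

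Section 7.3.3 names the uncorrected parameters but takes its residual from a model that 7.3 specifies only for adjusted ones. Two analysts could follow it in good faith and produce two different flag lists. At stake are which subjects are put forward for possible exclusion from the primary analysis and which are left out of the reference mean in the low-concentration rule. An ambiguity of this kind is best settled before any concentration is seen.

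**Working it through.** **1. What the wording asks for.** Two parameters times two analytes makes 4 screens. Only T4 is assayed, so 2 of the 4 cannot be computed. With T4 and the two adjusted parameters there are 2 screens, matching the two primary endpoints.

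**2. Which variable is meant.** The symbols in 7.3.3, read with 7.2 and Table 2, point to uncorrected data. The reference to the model, read with 7.3.2.1, points to adjusted data. No analysis of variance on uncorrected values is specified, so 7.3 supplies no error mean square for the parameters named. The two readings cannot both hold.

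**3. How often the list is used.** With clean normal data, the 7.3.3 formula and the ±2 cut, simulation (20,000 trials) flags about 1.8 of 44 subjects per parameter, with a 94 % chance of at least one. With 34 subjects it is about 1.4, with an 87 % chance. A non-empty list is therefore the expected result.

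**4. How far the lists could differ on the raw reading.** The protocol gives no between-period baseline variability, so inputs must be assumed.

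*What the protocol's figures imply.*
- Absorption 80 % of 600 µg is 480 µg. Divided by 11.6 L, this is 41.4 ng/mL.
- A half-life of 6.2 d is 148.8 h. The adjusted AUC0-48h is then 41.4 × (148.8/ln 2) × (1 - 2^(-48/148.8)) ≈ 1,780 ng·h/mL.
- If the 2004 study's AUC0-48h in Table 1 is uncorrected, the test-product baseline is (4,359.3 - 1,780)/48 ≈ 54 ng/mL.
- That study's Cmax gives 112.0 - 41.4 ≈ 71 ng/mL instead. The figures do not agree on one baseline, and Table 1 does not say whether its values are corrected.

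*Simulation A.* 34 subjects, adjusted CV taken as 23.7 %, raw AUC = 48 × baseline + adjusted AUC, between-period baseline CV assumed at 3, 5, 8 and 12 %, 3,000 trials per setting. Share of raw-AUC flags that are also adjusted-AUC flags:

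| Baseline / adjusted AUC | 3 % | 5 % | 8 % | 12 % |
|---|---|---|---|---|
| 54 / 1,780 | 0.66 | 0.60 | 0.53 | 0.41 |
| 75 / 760 | 0.44 | 0.31 | 0.19 | 0.11 |

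*Simulation B.* 44 subjects, baseline 70 ng/mL, dose increment 42 (Cmax-like, CV 17 %) or 22 (AUC-like, CV 20 %), baseline CV 3-10 %, baseline measurement error 2-4 %, 4,000 trials per setting. The raw screen finds 26-60 % of the adjusted flags for Cmax and 12-44 % for AUC. Both screens flag about 1.8-2.0 subjects, so the counts would not reveal the mismatch.

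**5. The denominator.** In a 2×2 crossover the intra-subject residual is half the deviation of a subject's period difference from its sequence mean. That difference has variance 2σ², so the residual variance is ¼ × 2σ² × (1 - 1/n_k) = σ²(n_k - 1)/(2n_k), where n_k is the number of subjects in that sequence. Section 7.3.3 uses the total S. The effective cut-off is:

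- 22 + 22: 2 × √(43/88) / √(21/44) = 2 × 0.6990/0.6908 = 2.02
- 17 + 17: 2 × √(33/68) / √(16/34) = 2 × 0.6966/0.6860 = 2.03

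With n_k, the flags per parameter on clean data move from 1.83 to 1.94 of 44, and from 1.38 to 1.49 of 34.

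**The case against.** The strongest reply is that the protocol as a whole points to adjusted data. The only model is for adjusted variables, so an analyst who follows 7.3.2.1 and then 7.3.3 would obtain adjusted residuals. The suffix is also dropped in 1.3, 4.5.2 and the Summary (12.3), so its absence may be house style. This stands to the extent that 7.3.3 cannot be read as a clear instruction to screen raw data. It does not clear the section. In 1.3 and the Summary the word corrected accompanies the plain symbols, and 7.3.1 to 7.3.2.3 say adjusted or carry the suffix. Where 7.3.3 names its parameters it does neither.

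A reader might infer that the trial will screen unadjusted values, flag the wrong subjects and remove them on endogenous variation. The documents do not support that. The text contradicts itself rather than prescribing it, and a flag is not a removal. Outlier exclusion needs scientific evidence, and a low-concentration exclusion also needs review by the health authority. No effect on the confidence interval, type I error or power has been shown.

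The simulated overlaps are also open to challenge. Section 7.1 gives 23.7 % for AUC0-72h without saying whether it is baseline-adjusted, and simulation A assumes perfect baseline correction. Both criticisms stand. The reference to two analytes changes no T4 result, since nothing else can be screened.

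**Conclusion.** The point holds as an incorrectly stated rule. Section 7.3.3 names uncorrected parameters and an unmeasured second analyte, against the model, the endpoints and the decision rule elsewhere in the protocol. Because 7.3.4 makes section 7.3 the statistical plan, this is not a detail simply left for later.

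The practical weight is small. The flags define candidates for exclusion and trim one reference mean; they do not remove subjects on their own. If raw values were screened, the list could differ substantially from the adjusted one under every set of assumptions tried. That applies only to the raw reading and rests on baseline inputs the protocol does not give, so no single figure should be quoted as the size of the defect. The S-for-n_k slip is algebraically real but secondary.

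**What to change.** In 7.3.3, state that studentised intra-subject residuals are computed for ln Cmax(aj) and ln AUC0-t(aj) of T4 from the 7.3.2.1 model, and delete the reference to two analytes. In the denominator, replace S with n_k, the number of subjects in that subject's sequence. This also handles unequal sequences after dropout.

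The cost is one sentence and one spreadsheet cell. Sample size, sampling and the decision rule are unchanged. Make the change before concentrations are available, so that the choice of screened variable cannot be questioned afterwards.

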7.3.4. Deviation to the Statistical Plan

The study statistical plan will correspond to what is specified in the section 7.3 of this protocol with regards to the methods and criteria for the statistical tests thus established to compare the bioavailability of the study drug.

All deviations should be justified by statistical or scientific evidence and any change should be reported in the original statistical plan, in the study master file and in the statistical pharmacokinetic report and study final report.

Subject data will not be replaced and any missing data will be considered as non-existent data. Likewise, data cannot be removed from the statistical analysis, except for the following cases:

- ⊕ Elimination of date due to vomiting and diarrhea.

Data from the research subjects who suffer from vomiting and diarrhea during the bioequivalence study for immediate release products can be removed from the statistical analysis if vomiting or diarrhea occurs before twice the median for t_{max} or twice the value for t_{max} from the research subject in a given period.

- ⊕ Research subject with very low serum concentrations for the study drugs.

As established by the NOM-177-SSA1-2013, also the research subjects who do not provide evaluable data in a crossed design, both for the test drug and for the reference drug, or who do not provide evaluable data in the single period of a parallel design, should not be included in the statistical analysis.

A research subject is considered to have very low concentrations, if the $AUC_{(a)}$ is $< 5\%$ for the geometric mean for the AUC of the reference drug (it should be calculated without including outliers). Exclusion of data for this reason, will only be accepted under scientific rationale and previous review of the case by the COFEPRIS.

- ⊕ Finally, all data which do not show significant outliers will be considered according to the criteria for outliers in the section 7.3.3 of this protocol. Outliers exclusion should be supported by scientific evidence.

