7.3. Statistical Analysis

7.3.1. Descriptive Statistics

Adjusted concentrations will be tabulated by treatment and by time of all subjects, stating the drug or formulation, the arithmetic mean, standard deviation and variation coefficient.

A descriptive statistic will be presented by the adjusted serum concentrations, by treatment globally (arithmetic mean, minimum value, maximum value, standard deviation and coefficient of variation).

The descriptive statistic will be determined from the individual adjusted pharmacokinetic parameters, by treatment, stating the period, sequence, quotient of the reference test, as well as its logarithm for the pharmacokinetic parameters used to determine the bioequivalence (geometric means, arithmetic mean, median, minimum value, maximum value, standard deviation and variation coefficient). This will only apply for evaluable subjects.

An evaluable subject will be one who has completed both periods of the study and has at least 60% of their samples with measurable concentrations, who has not presented vomiting or diarrhea before 2 times the median of the t_{max} or 2 times the value of t_{max} and who has not presented any situation that could modify the result of the study due to uncontrolled variables.

A graphic of the adjusted serum concentration against individual and average time in the arithmetic and semi-logarithmic scale.

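### Section 7.3.4 allows a subject to be removed for very low exposure on the test product, the failure this trial should detect, and requires no analysis that keeps the subject

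*Protocol*

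**What the plan says.** Section 7.3.4 forbids removing data from the statistical analysis except in listed cases. One case is headed "Research subject with very low serum concentrations for the study drugs". Its criterion reads "A research subject is considered to have very low concentrations, if the $AUC_{(a)}$ is" below 5% "for the geometric mean for the AUC of the reference drug (it should be calculated without including outliers"). No product or period is named for the low value; the reference product enters only as the yardstick.

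The same bullet, citing NOM-177-SSA1-2013, leaves out of the analysis "the research subjects who do not provide evaluable data in a crossed design, both for the test drug and for the reference drug". It ends with a safeguard: "Exclusion of data for this reason, will only be accepted under scientific rationale and previous review of the case by the COFEPRIS".

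Three other places bear on the rule:

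- Section 7.3.1 defines an evaluable subject as one who, among other conditions, "has at least 60% of their samples with measurable concentrations". It names no product either, so it does not narrow the rule.
- Section 7.3.3 flags as an outlier any value whose standardized intra-subject residual lies beyond ±2. The last bullet of 7.3.4 allows outliers to be excluded with scientific support and mentions no regulator review.
- Section 7.3.2.3 bases the decision on baseline-corrected parameters: "The statistical analysis to show interchangeability will be done using only the corrected values of the parameters".

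**The concern.** A bioequivalence trial exists to find out whether the test tablet delivers drug as the reference does. Near-zero exposure after the test tablet is the clearest evidence that it may not. A rule that lets such a subject leave the primary analysis selects the data on the test outcome and moves the estimated ratio back towards 1.

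The rule asks for no non-product cause, such as a dose not taken, and does not require that the low value lie in the reference period. It also asks for no analysis that retains the subject. The trial is open-label (4.1) and the Principal Investigator holds the randomization codes (4.4.9); the blinding described there covers the analytical unit. An exclusion request can therefore be prepared by someone who knows which product gave the low value. With a few dozen subjects, one removal can decide the result.

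**Working it through.** **Inputs.** From section 7.1: intra-subject CV 23.7% (AUC0-72h), difference 5%, power 90%, range 80–125%, 34 evaluable and 44 enrolled. From 7.3.2.3: the 90% confidence interval. Assumed for illustration: one subject with a test/reference ratio of 0.04, and a true ratio of 1.00 or 0.95 in the others.

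**The plan's own figures.** On the log scale, σ_w = √ln(1 + 0.237²) = 0.234. The crossover formula, n per sequence ≥ (t₀.₉₅ + t₀.₉₀)² × [σ_w / (ln 1.25 − ln 1.05)]², gives 34 in total. Then 34/0.8 = 42.5, so 43, or 44 with balanced sequences. The stated 34 and 44 reproduce.

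**Effect of one test-period failure at N = 34 (17 per sequence), ratio 1.00 in the others.**

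- Point estimate: multiplied by exp(ln 0.04 / 34) = exp(−3.219/34) = 0.910.
- Error mean square, expected: [31 × 0.234² + (16/17) × 3.219²/2] / 32 ≈ 0.205. Its root is 0.453, against 0.234 without the subject.
- Kept: standard error 0.453 × √(½ × 2/17) = 0.110; with t₃₂ = 1.694, the typical interval is 0.910 × exp(±0.186) = 0.755 to 1.096. The lower limit is below 0.80.
- Dropped: standard error 0.234 × √(½ × (1/16 + 1/17)) = 0.058; with t₃₁ = 1.696, the typical interval is about 0.907 to 1.102, well inside the range.

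**Proportion of trials concluding equivalence** (simulated 2×2 crossover, 40,000 trials per row):

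| N | Failure | True ratio in the others | Kept | Dropped |
|---|---|---|---|---|
| 34 | test, ratio 0.04 | 1.00 | 13% | 97% |
| 34 | test, ratio 0.04 | 0.95 | 2–3% | 90% |
| 44 | test, ratio 0.04 | 1.00 | 51–52% | 99% |
| 44 | test, ratio 0.04 | 0.95 | 16% | 96% |
| 34 | reference, ratio 25 | 1.00 | 13% | 97% |
| 34 | reference, ratio 25 | 0.95 | 34% | 90% |

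With two test-period failures at N = 34 and ratio 1.00, the figures are 0% kept and 96% dropped.

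**The other way out.** Under the 7.3.3 formula at N = 34, the failed subject's residual is ½ × (−3.219) × 16/17 = −1.515. The divisor is √[(33/68) × 0.205] = 0.316, so the standardized residual is about −4.8, far beyond ±2. The same subject could therefore be removed under the last bullet of 7.3.4, where no regulator review is mentioned.

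**The case against.** **Removal is not automatic.** The bullet requires a rationale and prior COFEPRIS review. This stands. The table compares always kept with always dropped and says nothing about how often such a subject occurs or how often the regulator would agree. The safeguard makes a biased removal less likely. It does not put test-product failures outside the rule, and it provides no analysis that keeps them.

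**The figures do not single out the test product.** This also stands. A reference-period failure gives the same 13% against 97% at ratio 1.00, because either kind of failure inflates the error variance. A reader might infer that the simulation proves a bias peculiar to test failures; it does not. The reason to treat the products differently is one of principle: a test-product failure is what the trial must detect.

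**N = 34 is the unfavourable end.** It assumes that the whole dropout allowance is used. With all 44 evaluable the gap is smaller, though still large.

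**A stronger reading that the document does not support.** The subject's AUC carries an adjusted marker and the benchmark AUC does not, while section 7.2 calculates both kinds: "They will be calculated with the uncorrected data of the baseline levels (raw values), as well as the corrected values by baseline levels (adjusted values"). A reader might infer that the cut-off is 5% of raw exposure and so much looser than it looks. A dropped subscript is far more likely. Sections 1.3 and 12.3 also omit the marker where corrected values are plainly meant, and 7.3.1 plans geometric means only for adjusted parameters. Any figure for the looser cut-off would also need an endogenous baseline, which the protocol does not give.

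**The wording may come from the standard.** The bullet refers to NOM-177-SSA1-2013, which is not at hand. Whether the standard sets the 5% rule, or allows a narrower one, could not be checked.

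**Conclusion.** The point holds. As written, 7.3.4 allows a subject to leave the primary analysis because exposure on the test product was very low, and it asks for no analysis that retains that subject. The effect favours a finding of equivalence.

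In the illustration, one removal takes the chance of concluding equivalence from about 13% to 97% (N = 34) or from 51–52% to 99% (N = 44) at a true ratio of 1.00 in the others. At 0.95 it goes from 2–3% to 90%, or from 16% to 96%. These figures rest on the protocol's CV for AUC0-72h, log-normal data, and an assumed single subject at a ratio of 0.04. They show what one decision can do and do not estimate how often it will be made. The case-by-case review lowers the seriousness. The rule should still be corrected before data are seen, because afterwards any choice would be made knowing the result.

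**What to change.** In 7.3.4:

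1. Limit the low-concentration exclusion to values in the reference-product period.
2. State that subjects with very low test-product AUC stay in the primary analysis, and that any analysis without them is a sensitivity analysis only.
3. State that such subjects may not be removed instead as outliers under 7.3.3 and the last bullet of 7.3.4. Without this, the first two changes can be bypassed.
4. Report results with and without any excluded subject.

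As a clarification only, write AUC0-t(aj) on both sides of the 5% cut-off. Because 7.2 sets negative adjusted values to zero, also say how an adjusted AUC of zero would enter the log-scale analysis.

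The cost is a few sentences, plus confirmation that the narrower rule agrees with NOM-177-SSA1-2013. The real downside is that a genuine dosing mishap in the test period could no longer be removed from the primary analysis on this ground; the sensitivity analysis would have to carry that argument.
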